## 8.0 Procedures Involved

### 8.1 Design/Study Type

**PROTOCOL TITLE:** *Development and Piloting of Avatar-based Intervention to Support Patients Undergoing Stem Cell Transplantation*

[figure not shown]
Aim 1: Focus group.

Aim 2: Single-arm feasibility pilot, with 3 cohorts of 6 patients (18 total).

## 8.2 care.coach

care.coach is a “human-in the-loop” conversational agent (avatar) used to interact and converse with patients through natural dialogue and text-to-speech software that is powered by a team of trained human staff, called health advocates. A summary of the platform is shown in [Figure 1](#). Note that the Family Portal and Provider Portal depicted in this figure are features from the commercial care.coach device that will not be activated for the purposes of this study. These features provide patient-avatar interaction summaries to the providers and, if approved by the patient, to family members.

**Figure 1.** care.coach Avatar Platform

[figure not shown]
The care.coach patient-facing interface appears as a virtual animal avatar on a touch-screen handheld device. Patients interact with the avatar by speaking with it or tapping the avatar on the screen. This simple interface allows many users to be engaged effectively. The avatar has two states: awake and asleep. When the avatar is visually sleeping, the audiovisual (AV) stream is offline. To awaken the avatar on-demand, it must be tapped on the touchscreen device. When the avatar is visually awake, the care.coach staff-monitored AV stream will become active. Several times per day, the avatar will attempt to engage the patient spontaneously to provide key reminders, such as for hydration or activity, and initiate patient education modules.

If a patient participant is not available, does not respond, or the participant requests privacy, the avatar will go back to sleep. Whenever the avatar is visually awake, care.coach staff members monitor the AV streams from the avatar device to hear, see and interpret what users are saying and what is happening in the environment. This enables the care.coach staff to speak to study participants

**PROTOCOL TITLE:** *Development and Piloting of Avatar-based Intervention to Support Patients Undergoing Stem Cell Transplantation*

appropriately and have genuinely natural, contextually relevant interactions and conversations. What the avatar says is guided by software protocols for consistency, speed, and automation, but is overseen and directly controlled (“supervised”) by care.coach staff to ensure that the avatar talks with patients in a sensible, appropriate, and empathic manner. In the case of an emergency when communicating with the avatar, the care.coach team will contact the unit coordinator (number will be provided at patient enrollment) and ask for the nurse assigned. A removable cover will be provided for the camera if patients desire at time of enrollment.

Health advocates contribute to the system their human abilities for natural language processing and compassionate conversational responses to help each avatar build personal relationships. While health advocates are not clinicians, they have a minimum set of certifications (Section 8.3).

*Figure 2: patient using the “tap to wake” feature on avatar*

Additionally, the abilities are augmented through a software-driven system embedded into the work interface, which guides participants through modules that aim to mitigate falls and delirium, executing cognitive exercises. Modules have been reviewed by principal investigators and will be adapted to best serve patients who have undergone RIC HCT. An analysis of the focus group on Aim 1 will result in the re-review and further improvement of these modules.

### **8.3 care.coach Health Advocate Training**

The health advocates who staff the avatar system must each complete the following screening mechanisms and training certifications (or their equivalents deemed by care.coach, as specific training courses and providers become outdated/available from time-to-time), through several online learning platforms, over the course of approximately 65 hours:

1. care.coach psychometric, technical, skills-based, and face-to-face interview assessment

**PROTOCOL TITLE:** *Development and Piloting of Avatar-based Intervention to Support Patients Undergoing Stem Cell Transplantation*

2. InfoCubic international background check
3. Registered Nurses' Association of Ontario delirium, dementia and depression course
4. National Institutes of Health privacy and ethics course for human subjects research
5. MGB basic motivational interviewing class
6. care.coach technology, patient support, information security, and job shadowing training

The qualification process is stringent, and the proportion of health advocate job applicants who successfully complete all the required certifications and are hired is only about 1%. For the proposed project, each health advocate will also attend a specific one-hour training about RIC HCT provided by Drs. [name] and [name].

#### **8.4 Study Procedures**

In Aim 1, a focus group consisting of focus group consisting of DF/BWH Cancer Center HCT nurse navigators, inpatient HCT nurses, and HCT physicians and extenders will be held to discuss the feasibility and benefits of implementing an avatar-based artificial intelligence system in an inpatient HCT setting (See Appendix B for draft script). The care.coach technology as described in Section 8.2 will be presented to the focus group. Following this introduction, a guided discussion will be held discussing the feasibility and benefits of providing this technology to HCT patients. Participants will receive \$50 gift cards for participation. The findings of this focus group will further shape the development of educational scripts incorporated into the care.coach technology.

In Aim 2, the care.coach device will be provided to a total of 18 patients (3 cohorts of 6 patients) who fall within the eligibility requirements outlined in Section 3.2 and who consent to participating in the study. Participants will receive the device while admitted at the Brigham and Women's Hospital for RIC HCT, and the device will be collected by study staff prior to discharge.

#### **8.5 Aim 2 Study Calendar**

**Table 1.** Study Calendar

Study Procedures	Baseline	Day 5 (<math>\pm 2</math>)	-1 to 0 days prior to discharge	One week after pilot (+ 5 days)
Informed Consent of participant	X			
Demographic data: self-report and EHR review	X			
Setting up avatar device	X			
RA check in		X	X	
Disenroll patients and retrieve avatar device from participants			X	

Post-pilot survey				X
-------------------	--	--	--	---

## 9.0 Data and Specimen Banking

9.1 **Data Collected by care.coach:** Only meta-data will be collected through the avatar device. care.coach will be provided with a first-name, study-assigned patient number, and in-hospital location for safety functions, but will not be provided with other PHI. Upon completion of the study, name and in-hospital location data will be decoupled from other data and destroyed by care-coach. Audiovisual streams are recorded for immediate language processing and understanding but will not be stored post-processing. See Appendix C for care.coach security protocols.

9.2 **Data Collected by Dana-Farber:** No specimens will be collected or stored as part of this study. We will collect data on feasibility outcomes (retention, satisfaction, completion of modules) via post-pilot survey administered by the RA in person, at first follow up at Dana-Farber after discharge, or via telephone (Appendix A). Components of post-pilot survey questions on technology usability (Q1-19) were adapted from a published system usability scale. Questions on self-efficacy (Q20-28) were directly adapted from the General Self-Efficacy Scale. The remaining questions were newly developed for this study. Data will also be collected on patient demographics, transplant characteristics (type of transplant, donor characteristics, conditioning, GVHD prophylaxis, antibiotic prophylaxis, status of prior infectious diseases), and transplant outcomes (incidence and severity of GVHD, other infectious and non-infectious complications, relapse, survival). PHI will be stored with these data to allow for monitoring of long-term outcomes. Data will be stored on a secure server at DFCI up to 5 years from completion of the last study conducted as part of this project (dependent on whether we proceed to the Phase 2 study). One year after completion of the study, long-term analyses, and publication of deidentified findings, all PHI will be destroyed.

9.3 **Data Storage:** No specimens will be stored.

**9.4 Data Sharing:** Aggregated de-identified post-protocol survey data will be shared with care.coach; care.coach meta-data will not be shared with DFCI.

## **10.0 Data Management and Confidentiality**

### **10.1 Data Analysis:**

Aim 1: This will be a qualitative study, consisting of a focus group of 8-10 subjects consisting of DF/BWH Cancer Center HCT nurse navigators, inpatient HCT nurses, and HCT physicians and extenders. The objective of Aim 1 is to use this focus group to identify key educational topics of interest, frequency of check-ins with the study patients, transplant treatment groups most likely to benefit from the avatar, timing of avatar device delivery, length of time with the avatar, and other potential uses for the avatar. After enrollment (as described in Section 5.0 ), we will undertake the focus group using a semi-structured guide (Appendix C), in which we will present each topic and ask for feedback. The focus group will be conducted either virtually using videoconference software or on-site at DFCI depending on the current state of the pandemic at the time of the focus group. The session will last approximately 60 minutes, will be audio-recorded, and will be transcribed verbatim. The interview guide will be further developed by the investigators, and we will consult the Dana-Farber/Harvard Cancer Center (DF/HCC) Survey and Data Management Core for help in reviewing our final guide (although we will run the focus groups ourselves). We will explore the themes listed in the Table in Appendix C, which have been developed based on areas of highest need in our transplant program to improve patient experience and outcomes. We will request feedback from the group about the utility of different transplant education topics, frequency of interruptions, and other potential uses of the avatar and recommendations for modifications to improve usability, feasibility, and utility of the avatar. In addition to soliciting feedback from all participants, we will perform in-depth explorations of components of the avatar functions for which each type of participant is considered a topical expert. For example, we will seek advice on optimal timing and frequency of patient interruptions from bedside transplant nurses who are most closely involved in direct patient care and are most familiar with patient needs and attention spans. The investigators will analyze all transcribed interviews through an interactive approach using framework analysis. Using techniques we have refined in prior work, two team members will review transcripts independently using an electronic research journal (NVivo 12 Pro) to create a coding matrix, after which they will compare results until reliability and interpretive consistency of coding is established (80% agreement). We will keep a thorough audit trail that will allow for other team members to carefully review and confirm that conclusions clearly flow from the coding, thus enhancing interpretive rigor and credibility. The study team will integrate

**PROTOCOL TITLE:** *Development and Piloting of Avatar-based Intervention to Support Patients Undergoing Stem Cell Transplantation*

findings from the focus group into the functions of the avatar to optimize the device functions for our patients.

**Aim 2:** We will enroll 18 patients in a single-arm pilot/feasibility study testing the care.coach avatar. The goal of the study is to determine if the avatar achieves the prespecified usability and feasibility outcome goals. As is common for HCT studies, the following covariates will be collected for each enrolled patient from hospital records and analyzed in conjunction with survey data collected by study RAs, with the support of the consulting biostatistician: incidence of delirium, falls, falls with injury, and sitter utilization, length of stay, use of benzodiazepines and sedatives, fluid “ins/outs” and meal fractions from nursing notes, in-hospital weights, neutrophil and platelet counts at fixed durations post-transplant, and incidence and severity of transplant-related complications including graft failure, graft-versus-host disease (GVHD), thrombotic microangiopathies (TMA), venous thrombosis, hemorrhage, acute infections and viral reactivations, idiopathic pneumonia syndromes, vaso-occlusive disease (VOD), cytokine release syndrome, mucositis, engraftment syndromes, and posterior reversible encephalopathy syndrome (PRES). Demographic variables between groups, including age, gender, education, and race/ethnicity collected upon enrollment will be compared to confirm equivalency and randomization. Primary and secondary usability and feasibility outcomes are summarized in Table 1. Each metric will be analyzed using paired t-tests to compare between groups and analysis of covariance to adjust for possible differences in demographics or initial assessments (baseline) between groups. Binary measures will entail chi-squared comparisons of proportions between groups. All data will be analyzed using the Statistical Package for Social Sciences software (SPSS, Inc. Chicago, IL). Statistical significance will be defined as  $p \leq 0.05$ .

**Table 2.** Usability and Feasibility Outcomes

Usability and Feasibility Outcomes	Estimated Percentage Usability or Feasibility
Determine the feasibility of retaining 18 patients in the protocol from enrollment to hospital discharge or three weeks (whichever comes first).	66%
Determine the patient satisfaction rate in the final cohort.	80%
Determine the rate of completion of the HCT educational modules.	75%
Determine the rate of completion of the post-pilot survey within one week of discharge.	90%

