## 6.0 Study Timelines

*Aim 1:* Prior to enrollment of the initial cohort of patients, we will convene a one-time 60minute focus group led by [name] PhD ([[name]\\[contact]](mailto:[contact])), a Senior Research Scientist in qualitative research, to discuss perspectives and opinions on implementing care.coach technology for HCT patients including education domains to include, frequency of avatar interactions, and anticipated staff concerns. This analysis will inform changes to be applied to the avatar, including script adjustments, prior to introducing the technology to patients in Aim 2.

*Aim 2:* We will complete the initial implementation of multiple HCT-related avatar changes across each of the categories in Section 2.2 and integrate them into an overall program schedule within 3 months. In the next 6 months, the HCT avatar program will then be piloted and iteratively improved through a phased, iterative user acceptance study with 3 consecutive cohorts of 6 RIC HCT patients each, receiving the avatar for up to 3 weeks per cohort (or patient discharge). After each cohort, user feedback will be gathered in the post-pilot survey (one week after disenrollment; see Appendix A), and protocol completion and patient-avatar engagement data will be analyzed.

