## **10.2 Sample Size:**

Aim 1: Aim 1. We selected a focus group size of 8-10 subjects. As per Krueger and Casey’s “Focus groups: A practical guide for applied research,” the ideal size of a focus group is 8-10 subjects because participants in a smaller focus group may feel pressure to talk more than they would otherwise, while larger focus groups will limit detail of participants’ responses who may feel pressure to share airtime.

Aim 2: A sample size of 18 patients was selected to achieve three goals. First, we estimated 162 RIC transplants per year over the past three years, with approximately 33% (54 patients) being performed inpatient, and estimated that approximately 33% could be enrolled, resulting in an achievable pilot sample size of 18 patients. Second, we ensured that the “rule of 10” for binary outcomes, wherein at least 10 participants per arm allows for reliable estimates in pilot studies (10 total in a single arm pilot, such as ours), was met. Third, we wanted to ensure that there were sufficient patients in three smaller cohorts to allow for an iterative process of improving the technology over the course of the pilot study, as per the guidance from the NIH SBIR process. With six patients per cohort, we should be able to achieve sufficient data for assessing usability.

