## **10.3 Milestones and Success Criteria:**

**PRIMARY:** Retention rate in protocol from enrollment to hospital discharge or three weeks (whichever comes first) of over 66%.

**SECONDARY:** Patient satisfaction rate with avatar in the final cohort of 80%; rate of completion of 80% of the HCT educational modules of 75%; rate of completion of post- pilot survey within 1 week of discharge of 90%.

**10.4 Risk Mitigation and Alternative Strategies:** After each group of 5 we will assess patient feedback and modify the avatar program; this iterative design will allow for rapid protocol improvements to be deployed to new patients in subsequent cohorts to move towards achieving the success criteria above. In case outcomes are disappointing during the first cohort, we may switch to a more frequent iteration rate, in conjunction with the advice of our consulting biostatistician.

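### Section 10.1 prescribes a randomization check, paired t-tests, ANCOVA and between-group chi-squared tests for a single-arm pilot, and gives no estimator or interval for the feasibility targets it is meant to judge

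*Combined protocol and SAP*

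**What the plan says.** Sections 4.0, 8.1 and 10.1 of the combined protocol and SAP describe Aim 2 as one group of 18 patients. Section 8.1 and the opening of the Aim 2 text in 10.1 call the study single-arm, and Section 6.0 says the patients arrive as "3 consecutive cohorts of 6 RIC HCT patients each". Section 10.2 defends the sample size partly by a rule of thumb under which "at least 10 participants per arm allows for reliable estimates in pilot studies (10 total in a single arm pilot, such as ours" – an argument about estimation in one arm. No comparison of groups enters the sample-size reasoning.

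Section 10.1 states the purpose plainly: "The goal of the study is to determine if the avatar achieves the prespecified usability and feasibility outcome goals". Its Table 2 lists four outcomes with percentages: retention 66%, satisfaction in the final cohort 80%, educational modules 75%, post-pilot survey 90%. The retention row reads, in part, "Determine the feasibility of retaining 18 patients in the protocol from enrollment to hospital discharge". Section 10.3 repeats these as success criteria, with retention to exceed 66%.

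The analysis prescribed in the same Aim 2 paragraph is of another kind:

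- Demographic variables between groups "will be compared to confirm equivalency and randomization".
- "Each metric will be analyzed using paired t-tests to compare between groups and analysis of covariance", the latter to adjust for demographic or baseline differences between groups.
- "Binary measures will entail chi-squared comparisons of proportions between groups".
- Significance is declared at p ≤ 0.05.

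No control group, allocation procedure or definition of the groups is given for Aim 2. No estimator, confidence interval or test against a target is given either.

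**The concern.** The methods are those of a two-arm randomized comparison, while the design and the stated goal are those of a one-sample feasibility study. An analyst who follows Section 10.1 faces two problems. Some of the prescribed steps cannot be carried out at all: there is no randomization to confirm and no between-group pairing. The step that can be carried out, a chi-squared test across cohorts, produces a p-value unrelated to whether a target was reached.

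At stake is what gets reported. The pilot could publish a check of a randomization that never took place, together with between-cohort p-values that a reader might take for evidence of feasibility or its absence. Meanwhile the quantity needed for planning the later randomized trial (mentioned in the Aim 2 text on potential benefits) is each rate and its uncertainty, and the plan does not ask for that uncertainty.

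**Working it through.** **1. The plan's own figure.** Section 10.2 takes 162 RIC transplants a year, about 33% inpatient, about 33% enrolled: 162 × 0.33 = 53.5 (stated as 54); 54 × 0.33 = 17.8; or 54/3 = 18. Three cohorts of 6 also give 18. The figure reproduces. It rests on accrual, a rule of thumb and cohort size; no power, effect size or precision is stated.

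**2. Can the prescribed methods be applied?** The only groups that the documents offer are the three cohorts. Section 10.4 uses the word in that way ("After each group of 5 we will assess patient feedback and modify the avatar program"; the 5 there does not match the 6 elsewhere, which is a separate matter). On that reading:

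| Method in 10.1 | What it needs | What Aim 2 has |
|---|---|---|
| Randomization check | Random allocation | Cohorts filled consecutively |
| Paired t-test between groups | Matched observations | Different patients in each cohort |
| ANCOVA between groups, adjusting for baseline | Groups and baseline assessments | No comparator; the study calendar (Section 8.5) shows demographics at baseline and a single survey after the pilot |
| Chi-squared between groups | Two or more groups per outcome | Possible for retention; impossible for the satisfaction target, which concerns the final cohort only |

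**3. Does a cohort chi-squared address the target?** For retained counts a, b, c out of 6 with total S, the expected retained count per cohort is e = S/3 and the expected lost count is 6 − e. Then X² = Σ(x − e)²/e + Σ(x − e)²/(6 − e) on 2 degrees of freedom, with p = exp(−X²/2).

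| Retained by cohort | Total | Over 66%? | X² | p |
|---|---|---|---|---|
| 4/4/4 | 12/18 = 66.7% | yes | 0 | 1.00 |
| 2/2/2 | 6/18 = 33.3% | no | 0 | 1.00 |
| 3/4/5 | 12/18 = 66.7% | yes | 1.5 | 0.47 |
| 2/4/6 | 12/18 = 66.7% | yes | 6.0 | 0.0498 |
| 6/6/6 | 18/18 = 100% | yes | undefined | none |

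For 2/4/6: e = 4, so X² = (4 + 0 + 4)/4 + (4 + 0 + 4)/2 = 2 + 4 = 6, and p = exp(−3) = 0.0498. The same total gives p from 0.0498 to 1.00, and totals on both sides of the target give p = 1.00. The p-value says nothing about the Section 10.3 decision.

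**4. What a one-sample analysis would show.** Exact (Clopper-Pearson) 95% limits for x of n are the 0.025 quantile of Beta(x, n − x + 1) and the 0.975 quantile of Beta(x + 1, n − x). At the smallest count that meets each target:

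| Outcome | Smallest passing count | Observed | Exact 95% CI |
|---|---|---|---|
| Retention, over 66% | 12/18 | 66.7% | 41.0% to 86.7% |
| Satisfaction, 80% | 5/6 | 83.3% | 35.9% to 99.6% |
| Modules, 75% | 14/18 | 77.8% | 52.4% to 93.6% |
| Survey, 90% | 17/18 | 94.4% | 72.7% to 99.9% |

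These assume that 18 enrol, that all six final-cohort patients answer, and that modules and survey use all 18 as denominator; the documents do not state the last.

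For context, the chance of at least 12/18 is 0.12 if true retention is 50%, 0.37 at 60%, 0.58 at 66% and 0.86 at 75% (binomial tail).

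**The case against.** The best defence is that little depends on these sentences. Section 10.3 gives plain percentage criteria, Section 10.1 states the goal and lists the percentages in Table 2, and a consulting biostatistician supports the analysis. All of that stands, and it limits the consequence: the success decision can be made without any of the tests. It does not make the randomization check or the between-group pairing valid.

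Cohort comparisons also have a legitimate use. The Aim 2 text on potential benefits wants the effect of the cohort 3 gift card assessed. That supports looking at results by cohort. It does not turn such a contrast into a test of a target, and the avatar may also have been modified between cohorts.

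Several stronger readings are tempting, and the documents do not support them:

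- *That the go/no-go decision is unsound or undefined.* A rate over 66% reads naturally as a rule on the observed percentage, and nothing mentions a confidence limit. There is no reason to suppose that the plan intends a lower limit to clear 66%.
- *That small cells make the chi-squared test badly misleading.* Expected counts are indeed low: the smallest in a 6/6/6 table never exceeds 3. But the actual error rate of the three-cohort test at a nominal 5% is about 5.7% at a common rate of 50%, 6.0% at 66%, 4.1% at 80% and 1.5% at 90%. The inflation is modest; the objection is that the test answers another question.
- *That t-tests and ANCOVA fit nothing in the study.* Section 10.1 sends binary measures to chi-squared and also lists non-binary data such as length of stay, weights and blood counts. These methods are not excluded there by the type of variable; what is missing is a defined pair of groups.

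**Conclusion.** The point holds and should be fixed. Section 10.1 prescribes, for a single-arm study, a check of randomization and between-group paired tests that cannot be valid on any reading, and a chi-squared comparison that does not bear on the stated goal. It names the targets but gives no estimator or interval for them.

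The size is moderate. The reported analysis would be invalid or irrelevant, and the precision goes unstated: a retention result that just meets its target is compatible with true retention anywhere from 41% to 87%, and a satisfaction result that just meets its target with 36% to 99.6%. The Section 10.3 decision is not shown to be wrong.

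The conclusion about pairing and randomization needs no numerical assumption. The chi-squared illustrations assume that the undefined groups are the three cohorts of 6. That is an inference, though no other groups are on offer.

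**What to change.** In Section 10.1 (Aim 2), delete the equivalency and randomization check. Also delete the paired t-tests and ANCOVA between groups, and the between-group chi-squared tests with p ≤ 0.05, as the analysis of the feasibility outcomes. Replace with:

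> Each feasibility outcome is reported as an observed proportion with an exact (Clopper-Pearson) 95% CI, and the observed proportion is compared with its Section 10.3 target. The CI shows precision and is not the decision rule. The denominator for retention is all enrolled patients; satisfaction uses the final cohort. Demographics, clinical covariates and any by-cohort results are summarised descriptively.

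The percentage should govern rather than a fixed count, because 18 is an anticipated enrolment.

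In Section 10.2, add the expected precision as an illustration: 41% to 87% at 12/18 (the smallest count over 66% if 18 enrol), and 36% to 99.6% at 5/6 if all six final-cohort patients respond.

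The cost is protocol text only, with no change to sample size or procedures. Between-cohort p-values are no longer reported, and the stated precision looks less favourable than an unqualified appeal to reliable estimates.

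Some matters are separate and are not settled by this text: how satisfaction and module completion are measured, and which module threshold a gift-card contrast would use (4 of 7 modules in the text on benefits, 80% of modules in Section 10.3). Whether the module data will reach the study site is also open, since Section 9.4 says the vendor's meta-data will not be shared with it.
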